4. STUDY DESIGN

This is an open-label pharmacokinetic study in 16 healthy Thai subjects. Subjects will be admitted in the inpatient ward and will be randomized to **group A** or **group B** to receive 3 drug regimens described in the following table 1. Every subject will have 1 screening and 3 admissions in the hospital.

Visit 1	Screening					
	Within 14 days					
	Group A (n = 8)	Group B (n = 8)				
Visit 2	Regimen 1	Regimen 2				
	Artemether-lumefantrine	Amodiaquine				
	on Day 0, 1, and 2	on Day 0, 1 and 2				
	Washout period: > 6 we	eeks (after day 3)				
Visit 3	Regimen 2	Regimen 1				
	Amodiaquine	Artemether-lumefantrine				

 Table 1: Study Schedule

	on Day 0, 1 and 2	on Day 0, 1 and 2		
Washout period: > 6 weeks (after day 3)				
Visit 4	Regimen 3			
	Artemether-lumefantrine + Amodiaquine on Day 0, 1 and 2			

The total duration for each subject's participation in the study is approximately 6 - 8 months depend on washout period. Study duration is approximately 12 months.

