5. STUDY POPULATION

5.1. Number of Subjects

This study will enroll 16 healthy subjects both male and female, aged 18-60 years, at the pharmacokinetic unit Faculty of Tropical Medicine, Mahidol University. Subjects will be healthy HIV-1, hepatitis B and C uninfected individuals who comprehend the purpose of the study and have provided written consent. All subjects will undergo screening assessments (visit 1). Screening assessments (visit 1) may be carried out over more than one day, provided that all required assessments are completed within the 14 days prior to visit 2. If the interval between screening (visit 1) and day -1 visit 2 is three days or less, the clinical laboratory screening test result and serum pregnancy test result can be used for enrolment evaluation on day -1 visit 2. In such cases, these tests would not need to be repeated at day-1 visit 2.

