- Chemistry, Hematology and urinalysis assessment
- Urine pregnancy test (if applicable)
- Pharmacokinetic sample collection
- ECG

Visit 4

Day -1 (admission)

- Physical Examination and symptoms questionnaire assessment
- Chemistry, Hematology, FBS and urinalysis assessment
- 24-hour urine for creatinine clearance test
- Vital signs will be checked every 4 hours.
- ECG monitoring according to table 2
- Holter monitoring (~30 mins baseline recording)
- Urine pregnancy test (if applicable)

Day 0-3 (admission)

- Daily physical examination and symptoms questionnaire assessment
- Vital signs will be checked before and every 4 hours after first dose.
- ECG monitoring according to table 2
- Continuous Holter monitoring during admission.
- Pharmacokinetic samples will be collected according to table 2
- Study drug administration (Artemether-lumefantrine AND Amodiaquine) will be given according to table 1.
- 24-hour urine for creatinine clearance test (Day 2)
- Chemistry, Hematology, FBS and urinalysis assessment before discharge

Day 4 (+1) (follow up)

- Physical Examination, vital signs and symptoms questionnaire assessment
- Pharmacokinetic sample collection
- ECG

Day 7 (+/-2d) (follow up)

- Physical Examination, vital sign and symptoms questionnaire assessment
- Chemistry, Hematology and urinalysis assessment
- Pharmacokinetic sample collection
- ECG
- Holter monitoring (~ 30 mins)

Day 14 (+/-2d) (follow up)

- Physical Examination, vital signs and symptoms questionnaire assessment
- Chemistry, Hematology and urinalysis assessment
- Urine pregnancy test (if applicable)
- Pharmacokinetic sample collection
- ECG

Day 21 (+/-2d) (follow up)

- Physical Examination, vital signs and symptoms questionnaire assessment
- Chemistry, Hematology and urinalysis assessment
- ECG

Day 28 (+/-2d) (follow up)

- Physical Examination, vital signs and symptoms questionnaire assessment
- Chemistry, Hematology and urinalysis assessment
- Urine pregnancy test_(if applicable)
- Pharmacokinetic sample collection

- ECG
- Holter monitoring (~ 30 mins)

Day 35 (+/-2d) (follow up)

- Physical Examination, vital signs and symptoms questionnaire assessment
- Chemistry, Hematology and urinalysis assessment
- ECG

Day 42 (+/-2d) (follow up)

- Physical Examination, vital signs and symptoms questionnaire assessment
- Chemistry, Hematology and urinalysis assessment
- Urine pregnancy test (if applicable)
- Pharmacokinetic sample collection
- ECG

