Appendix 2 Fime and Events Table

1. Vital signs will be measured before dosing and every 4 hours after first dose. Blood pressure (BP) and heart rate (HR) for visit 2-4 will be measured in both the supine and standing positions in each time-points

- 2. Serum pregnancy test will be done at screening visit
- 3. Urine pregnancy test will be done at day -1 for each admission visit and biweekly during follow up visit
- 4. ECG (x3) will be performed according to table 2
- 5. Clinical lab assessment will be performed at screening visit (visit 1), day -1 and day 3 of each admission visit (visit 2-4) and weekly during follow up visit (see appendix 4 for the detail)
- 6. PK sample will be collected according to table 2 and appendix 4
- 7. Study drug administration will be administered according to table 1 and 2 and appendix 3
- Genetic sample can be collected at any of the subsequent visit if the blood draw at the visit 2 is missed
 Adverse events will be monitored until the last follow up visit.
- 10. Concomitant medications will be monitored until last follow up visit.
- 11. If interval between screening (visit 1) and on day -1 visit 2 is three days or less, the clinical laboratory screening test result and serum pregnancy test result can be used for enrolment evaluation on day -1 visit 2. In such cases, these tests would not need to be repeated at day-1 visit 2.
- 12. Holter monitoring will be performed on day -1, admission visit, D7 and D28 of visit 2, visit 3, and visit 4

Appendix 3

Drug dosing schedule

Artemether-lumefantrine dosing schedule								
One tablet A/L contains 20 mg artemether and 120 mg lumefantrine.								
	No. of tablets recommended at approximate timing of dosing							
Weight:	:: 0 h 8 h 24 h 36 h 48 h 60 h							
≥35 Kg	4	4	4	4	4	4		

Amodiaquine dispersible tablets dosing schedule						
One tablet contains 76.5 mg Amodiaquine.						
	No. of tablets recommended at approximate timing of dosing					
Weight:	0h	8h	24h	36h	48h	60h
35-41 Kg	2	2	2	2	2	2
42-55 Kg	3	3	3	3	3	3
≥ 56 Kg	4	4	4	4	4	4

Appendix 4

Total Blood Collection

visit		laboratory assessments	PK Sampling	Blood sampling	
Visit 1	Screening visit Clinical lab (Chemistry and Serum pregnancy test, HIV, Hep B, Hep C and TSH 6 mL, Hematology 2 mL, FBS 2 mL) (Total 10 mL)	10 mL	0	10 mL	
Visit 2	Day-1 (admission) Clinical lab (Chemistry 5 mL, Hematology 2 mL, and FBS 2 mL) (Total 9 mL)	9 mL	0	85 mL (Artemether - lumefantrine only)	

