3.5 STUDY ASSESSMENTS
3.5.1 Demographics and other baseline characteristics

The baseline summaries will include the below variables (Table 1), stratified by group.

Table 1. Demographic and other baseline characteristics at the time of crossover

Characteristic	AL → AQ → AL+AQ	AQ → AL → AL+AQ
Age (years)		
Median (IQR)		
Sex: female n(%)		
Weight (kg)		
Median (IQR)		
Height (cm)		
Median (IQR)		
Body Mass Index (kg/m ²)		
Mean(sd)		
Haemoglobin (g/dL)		
Mean(sd)		
WBC (10 ³ /uL)		
Median (IQR)		
Platelet count (10 ³ /uL)		
Median (IQR)		
Neutrophil count (%)		
Median (IQR)		
ALT (U/L)		
Median (IQR)		
AST (U/L)		
Median (IQR)		
Creatinine (mg/dL)		
Median (IQR)		
XXXX		

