3.5.3 Safety assessments

The incidence of AEs will be tabulated and reviewed for potential signals and clinical importance. The most prevalent AEs will be reported by group: (AL → AQ → AL + AQ) vs (AQ → AL → AL + AQ). Any Serious Adverse Events (SAEs) including any deaths will also be reported by group. Standard haematological parameters, serum chemistries, liver and renal function test results at screening and post-treatment will be summarised across the treatment groups. For the safety data such as adverse events, proportions will be compared using Fisher's exact test and a significance level of 5% where appropriate.

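### SAP 3.5.3 names screening as the only pre-treatment laboratory value, so AL+AQ, always given third, has no pre-dose comparator of its own in the planned summary

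*SAP*

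**What the plan says.** SAP 3.5.3 gives laboratory safety one sentence, covering haematology, serum chemistry, and liver and renal function: "liver and renal function test results at screening and post-treatment will be summarised across the treatment groups". Just before it, the same paragraph says "The most prevalent AEs will be reported by group" and lists the groups as AL → AQ → AL+AQ and AQ → AL → AL+AQ. No change from baseline is defined there. Protocol 12.5.2 adds none: it calls for descriptive summaries and as-treated analysis.

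The protocol collects more than the SAP uses. Appendix 2, note 5, says "Clinical lab assessment will be performed at screening visit (visit 1), day -1 and day 3 of each admission visit", with weekly draws in follow-up. Section 6.1.2 lists "Chemistry, Hematology, FBS and urinalysis assessment" on Day -1 of Visits 2, 3 and 4.

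Screening happens once; section 5.1 requires that "all required assessments are completed within the 14 days prior to visit 2". Protocol section 4 and SAP 2.5 place AL+AQ third for every subject, with a washout of more than 6 weeks after Day 3 before each of Visits 3 and 4. SAP Table 1 is titled "Demographic and other baseline characteristics at the time of crossover".

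**The concern.** Each regimen has its own pre-dose sample, but the SAP names none of them. The only pre-treatment value that it names precedes all study drug. For Visit 2 this matters little, because screening is recent. For AL+AQ the named value predates both the AL and the AQ course.

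Safety and tolerability of the co-administered drugs are a stated secondary objective. A table that sets screening beside post-treatment values cannot say whether a difference seen at Visit 4 arose during AL+AQ or was already present on Visit 4 Day -1. If results are pooled by sequence, each column contains all three regimens and the combination may not be visible.

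**Working it through.** The plan gives no figure to reproduce. The check is of elapsed time, of what lies between the two time points, and of what post-treatment could mean.

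**1. Shortest gap.** Take Visit 2 Day 0 as day 0 and each washout at its minimum of 42 days after Day 3 (protocol section 4).
- Visit 3 Day 0: 3 + 42 = day 45.
- Visit 4 Day 0: 45 + 3 + 42 = day 90.
- Screening 1 to 14 days before Visit 2 Day 0 (the 14 is from section 5.1; the 1 is an assumption): screening to Visit 4 Day 0 is 90 + 1 = 91 to 90 + 14 = 104 days, or 3.0 to 3.4 months.

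**2. Gap implied by the stated duration.** Section 4 says "The total duration for each subject's participation in the study is approximately 6 - 8 months". Subtract the 42-day follow-up of Visit 4, at 30.4375 days per month.
- 6 months: 182.6 − 42 = 140.6 days = 4.6 months.
- 8 months: 243.5 − 42 = 201.5 days = 6.6 months.

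**3. Distance from reference value to the Visit 4 Day 3 sample (day 93).**
- From screening, at minimum washouts: 93 + 1 = 94 to 93 + 14 = 107 days, with both earlier courses in between in either sequence.
- From Visit 4 Day -1: 4 days, with no earlier course in between.

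**4. What can shift between screening and Visit 4 Day -1.**
- Carry-over: protocol section 10.3 requires values to return to limits before the next round, namely blood counts in the normal range and biochemistry below 1.5 × ULN. Movement inside those limits is allowed.
- Residual drug: the protocol introduction gives desethylamodiaquine a half-life of 9 to 31 days. After 42 days the remaining fraction is 2^(−42/9) ≈ 4% to 2^(−42/31) ≈ 39%. Group A takes AQ immediately before Visit 4. Residual drug does not prove a residual laboratory effect.
- Blood draws (Appendix 4): 10 screening + 85 AL + 100 AQ = 195 mL before Visit 4, or 205 mL if the 10 mL genetic sample has been taken.

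**5. How many draws could count as post-treatment.** Scheduled post-dose laboratory draws are 5 after AL (Days 3, 7, 14, 21, 28) and 7 each after AQ and AL+AQ (the same plus Days 35 and 42). That makes 5 + 7 + 7 = 19 per subject, and the SAP does not say which are meant.

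**6. What a Day -1 baseline does not remove.** Blood drawn from Day -1 to Day 3 is 9 + 70 + 9 = 88 mL at Visit 4, against 9 + 35 + 9 = 53 mL in a single-regimen period. The 35 mL difference still falls on AL+AQ.

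**The case against.** The strongest reply is that the SAP sentence is under-specified rather than wrong. A reader might infer that changes under AL+AQ will be calculated from screening, and that all drift will therefore be charged to the combination. The documents do not support that. No change score is planned, and charging drift to AL+AQ presupposes a by-regimen display that SAP 3.5.3 does not define. Under grouping by sequence, both columns end with AL+AQ, and drift by Visit 4 would fall on both in much the same way.

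Safeguards also exist. Protocol 6.1.2 requires laboratory results to be reviewed before Day 0 dosing, section 10.3 sets limits before the next round, and section 11.2 has abnormal findings reported as adverse events. Detection of marked laboratory harm does not rest on this table alone.

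A reader might also infer a large spurious haemoglobin fall or ALT rise. Such figures need assumptions that the documents do not supply, for example no red-cell replacement over three months or more, or an ALT sitting just under the permitted limit. They are not evidence of size.

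Lastly, the Table 1 title could be read as placing baseline after the first regimen. SAP 3.3.1 ties most baseline variables to the eligibility criteria, so this is mainly a loose label.

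These replies limit the consequence but do not meet the core point: the SAP names no pre-dose value for Visits 3 or 4 and no display that isolates AL+AQ.

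**Conclusion.** The concern holds as a weakness in the planned laboratory summary. Followed as written, the summary gives AL+AQ a pre-treatment comparator at least 91 to 104 days old at first dose (about 4.6 to 6.6 months on the stated participation), taken before two other drug courses. It may not show AL+AQ separately at all. It cannot distinguish the combination's laboratory effect from carry-over within the section 10.3 limits, drift or earlier blood draws.

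The gap rests on the washout rule, the stated duration, and screening 1 to 14 days before Visit 2 Day 0. The size of any resulting distortion cannot be estimated from the documents. The point concerns a descriptive safety table in 16 subjects. Sample size, error rates and the primary pharmacokinetic analysis are unaffected. It should be corrected because safety of the combination is a secondary objective and the better comparator is already being collected.

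**What to change.** In SAP 3.5.3, replace the screening and post-treatment summary with the following:
- Summarise laboratory values, and change from that admission's own Day -1, by regimen (AL, AQ, AL+AQ), at Day 3 and each follow-up day with a scheduled draw. All three regimens can be compared to Day 28; Days 35 and 42 exist only for AQ and AL+AQ.
- Use screening as the Visit 2 baseline only where Visit 2 Day -1 tests are waived because screening was three days or less earlier. Otherwise keep screening as a descriptive column.
- State that haemoglobin changes are to be read alongside the 88 mL against 53 mL drawn between Day -1 and Day 3.

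As a minor edit, retitle Table 1 so that baseline is clearly before any study drug.

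The cost is SAP wording and table shells. No sample, visit or subject is added.
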